10.2.2. Demographic and Other Disease Characteristics

Descriptive statistics were performed on sociodemographic characteristics and other disease characteristics. Sociodemographic characteristics include age, sex, etc. Other characteristics include tumor history and past medical history.

10.2.3. Analysis of Primary Study Endpoint

The primary endpoint of this study is pathological response rate, which will be aggregated and its 95%CI.

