3.1 Experiment Design

This is a single-institution, single-arm phase II clinical trial. Patients with histopathologically or cytologically confirmed colon adenocarcinoma without distant metastases (T4 or T3 with extramural depth ≥ 5 mm, N₀₋₂, M₀, AJCC 8th) were enrolled.

Patients with microsatellite-stable or proficient mismatch repair (pMMR) received 5 cycles of mFOLFOX6 and camrelizumab (200 mg intravenously on day 1, every 2 weeks) and apatinib (250 mg orally once daily, 2 months). mFOLFOX6 consisted of oxaliplatin 85 mg/m² on day 1, leucovorin 400 mg/m² on day 1, fluorouracil 400 mg/m² bolus on day 1, followed by fluorouracil 2,400 mg/m² continuous infusion over 46 hours, repeated once every 2 weeks. Surgery was scheduled within 4-6 weeks after the last cycle of therapy. 7 cycles of adjuvant camrelizumab plus mFOLFOX6 were administered after surgery.

For patients with microsatellite-instability-high (MSI-H) or deficiency in mismatch repair (dMMR), 5 cycles of camrelizumab (200 mg intravenously on day 1, every 2 weeks) plus apatinib (250 mg orally once daily, 2 months) were given preoperatively and 7 cycles of camrelizumab plus apatinib were given postoperatively.

Tissue samples and peripheral blood samples were collected for further multiomics analysis. The sampling points were: (1) Peripheral blood and colonoscopy tumor tissue at baseline; (2) Peripheral blood before operation; (3) surgical tumor tissue; (4) Peripheral blood 1 month after surgery (5) Peripheral blood after adjuvant chemotherapy

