3.2 Sample Size

To determine the sample size, we used the Simon 2 stage optimum design with unilateral alpha 0.05 to achieve the power of 0.8, the pathological response rate (TRG 2-4) is expected to increase from 22.5% to 40%. Considering a 10% shedding rate, it is estimated that 64 patients will need to be enrolled.

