5.3 Primary Study Endpoint

Tumor regression rate of MSS/pMMR patients (Pathological response, percentage of TRG2-4 to all MSS patients, Dworak criteria)

TRG Dworak criteria: Grade 0: no regression; Grade 1: dominant tumor mass with obvious

fibrosis and/or vasculopathy; Grade 2: dominantly fibrotic changes with few tumor cells or groups (easy to find); Grade 3: very few (difficult to find microscopically) tumor cells in fibrotic tissue with or without mucous substance; Grade 4: no tumor cells, only fibrotic mass (total regression or response).

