Statistic Analysis Plan

Title of study	Neoadjuvant chemotherapy combined with camrelizumab and apatinib in patients with locally advanced colon cancer: a single-arm, prospective study
NCT number	NCT04625803
Institution	The First Affiliated Hospital, Zhejiang University School of Medicine
major investigators	[name] [name]
Protocol No.	MA-CRC-II-004
Version	1.3
Version Date:	07 November 2021

1.sample size

This was a single-arm study, and no randomization was used. To determine the sample size, we used the Simon 2-stage optimum design with a unilateral alpha of 0.05 to achieve a power of 0.8, and the pathological response rate (TRG 2-4) was expected to increase from 22.5% to 40%. Considering a 10% shedding rate, it was estimated that 64 patients needed to be enrolled.

2. Subject Distribution

Descriptive analysis of subject distribution, including but not limited to enrollment, withdrawal, and major protocol violations. The reasons for screening failure and the reasons for quitting the test were summarized.

3. Demographic and Other Disease Characteristics

Descriptive statistics were performed on sociodemographic characteristics and other disease characteristics. Sociodemographic characteristics include age, sex, etc. Other characteristics include tumor history and past medical history.

4. Analysis of Primary Study Endpoint

The primary endpoint of this study is pathological response rate, which will be aggregated and its 95%CI.

5. Secondary Study Endpoint Analysis

For the temporal event data (DFS, OS) in the secondary endpoints, Kaplan-Meier was used to estimate the median value, estimate the 95%CI of the median DFS/OS, plot a survival curve, and estimate the 2-year disease-free survival and its 95%CI.

Statistical rates and 95%CI were pooled for binary data in secondary endpoints (tumor pathological downphase rate, pCR rate, and R0 removal rate).

6. Safety Analysis

All the statistical analyses were performed using SPSS Statistics 26 (IBM, Armonk, NY, USA). Continuous variables with parametric distributions were evaluated using t tests. Categorical variables were evaluated using the chi-square test (or Fisher's exact test where appropriate). All the statistical tests were two-sided, and the significance threshold for all the P values was 0.05. Graphs were generated using GraphPad Prism (version 10.1.1).

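### The planned primary analysis (a rate with a 95% CI) does not carry out the one-sided Simon two-stage test that justifies N=64, and no decision rule is stated

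*Protocol*

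**What the plan says.** **Sizing.** Protocol 3.2 states that "we used the Simon 2 stage optimum design with unilateral alpha 0.05 to achieve the power of 0.8", with a null response rate (TRG 2-4) of 22.5% and a target of 40%. It continues: "Considering a 10% shedding rate, it is estimated that 64 patients will need to be enrolled". SAP section 1 repeats this: "we used the Simon 2-stage optimum design with a unilateral alpha of 0.05 to achieve a power of 0.8". Neither document prints the stage-1 size, the stage-1 boundary or the final number of responders required.

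**Analysis.** Protocol 10.2.3 reads "The primary endpoint of this study is pathological response rate, which will be aggregated and its 95%CI", and SAP section 4 repeats it. Protocol 10.2 sets every interval at 95% and names no interval method. SAP section 6, headed Safety Analysis, says that all statistical tests were two-sided with a 0.05 threshold.

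**Population.** Protocol 5.3 defines the primary endpoint as the "percentage of TRG2-4 to all MSS patients". Protocol 3.1 also enrols a second group: "For patients with microsatellite-instability-high (MSI-H) or deficiency in mismatch repair (dMMR), 5 cycles of camrelizumab" and apatinib are given without chemotherapy. The documents do not say whether the 64 are MSS/pMMR patients only.

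**The concern.** A Simon design is a decision procedure: a look after stage 1, then a fixed responder count tested one-sided against the null rate. Its alpha and power hold only if both parts are carried out. The analysis sections carry over neither part and do not mention 22.5%. What they plan is a two-sided 95% interval, which is stricter than a one-sided 5% test if it is set against the null rate.

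In a single-arm trial the prespecified threshold is the main protection against choosing the reading after the result is known. Here a final count of 18 or 19 of 57 could be reported as a success by the sizing rule, or as an interval that does not exclude 22.5%. Depending on which parts are applied, the error rates also differ from those stated.

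**Working it through.** **Inputs.** p0 = 0.225, p1 = 0.40, one-sided alpha 0.05, power 0.80, 10% dropout, N = 64 (Protocol 3.2, SAP section 1); 95% intervals (Protocol 10.2).

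**1. Reproduce 64.** For a design with n1, r1, n and success at r or more responders,

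P(success | p) = Σ over x from r1+1 to n1 of b(x; n1, p) × P(Y ≥ r − x), with Y ~ Bin(n − n1, p).

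An exact search over all designs with alpha ≤ 0.05 and power ≥ 0.80, minimising expected N under p0, gives n1 = 19, r1 = 5, n = 57, success at 18+:
- alpha 0.0499, power 0.8041;
- probability of stopping early: 0.758 at 22.5%, 0.163 at 40%;
- expected N under p0: 19 + 38 × (1 − 0.758) = 28.2;
- 57/0.9 = 63.3, rounded up to 64, as stated.

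The minimax design (4/19, 14/44) would give 44/0.9 = 48.9, so 49. The printed 64 therefore supports the optimum design and its boundaries.

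**2. Where the interval excludes 22.5%.** Lower 95% limits at n = 57:

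| Responders | Clopper-Pearson | Wilson | Wald |
|---|---|---|---|
| 18 | 19.9% | 21.0% | 19.5% |
| 19 | 21.4% | 22.49% | 21.1% |
| 20 | 22.9% | 24.0% | 22.7% |

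All three methods need 20 responders. An exact test agrees: the single-stage upper tail at 22.5% is 0.0402 for 19+ and 0.0207 for 20+, so only 20+ falls below 0.025.

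**3. Error rates of each possible reading, n = 57.**

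| Rule | Alpha at 22.5% | Power at 40% |
|---|---|---|
| Look, then 18+ (Simon) | 4.99% | 80.4% |
| Look, then 95% CI (20+) | 1.6% | 73.0% |
| 18+ without the look | 7.3% | 92.6% |
| 95% CI (20+) without the look | 2.1% | 81.3% |
| Single-stage exact 0.05 rule (19+) | 4.0% | 87.8% |

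At a true 40%, the two-stage trial ends at 18 or 19 responders with probability 0.8041 − 0.7303 = 0.0738, about 7.4%.

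**4. If more than 57 are analysed.** Keep 5/19 and take the smallest final count with two-stage alpha ≤ 0.05:

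| N | Success at | Alpha | Power |
|---|---|---|---|
| 58 | 19+ | 3.4% | 78.7% |
| 59 | 19+ | 3.9% | 79.6% |
| 60 | 19+ | 4.4% | 80.4% |
| 61 | 19+ | 5.0% | 81.1% |
| 62 | 20+ | 3.5% | 79.7% |
| 63 | 20+ | 4.0% | 80.5% |
| 64 | 20+ | 4.5% | 81.1% |

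Over N = 57 to 64, the look followed by an exact 95% CI has power 69.3% to 75.5%.

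**The case against.** The strongest reply is that a descriptive interval beside a design-based test is ordinary practice. On this view the sample-size section supplies the rule, 10.2.3 describes reporting, and the boundaries follow uniquely from the inputs. A two-sided 95% interval and a one-sided 5% test will disagree near the boundary because their levels differ, and that alone is not a contradiction.

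Much of this stands. The rule is recoverable and, carried out as designed, meets its targets. A reader might infer from the 73.0% that the trial is underpowered. The documents do not support that: the figure needs a criterion (lower limit above 22.5%, or two-sided 0.05) that they never state for the primary endpoint, added to the stage-1 stop. Without the look, the interval has power 81.3% at n = 57. A reader might also take the SAP's two-sided sentence as governing the primary endpoint. It says all tests, but it sits under Safety Analysis, and SAP section 4 names no test. Nor does the text show that the look was left out; it is silent.

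What does not stand is that nothing is missing. The analysis sections do not refer to the design, the null rate, the look or a boundary, and the only sentence on test level points to two-sided 0.05. A reader who rebuilds 5/19 and 18/57 still cannot tell whether they decide.

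**Conclusion.** The concern holds as a mismatch between the sizing and the planned analysis, and it should be fixed. At n = 57 it concerns two outcomes, 18 and 19 responders, reached in about 7.4% of two-stage trials at a true 40%. The two mixed readings miss a stated target: power 73.0% instead of 80% for the look plus CI, and alpha 7.3% instead of 5% for 18+ without the look. The two unmixed readings, Simon alone and CI alone without a look, meet both targets at n = 57.

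Assumptions: the boundaries are recovered from the inputs, not printed; n is the number of MSS/pMMR patients in the primary analysis; and the CI figures take success to mean a lower limit above 22.5%. If MSI-H/dMMR patients count towards the 64, fewer than 57 may be available. The documents give no MSI-H share, so no size is put on that.

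**What to change.** In Protocol 10.2.3 and SAP section 4:

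- State that the primary test is the one-sided 0.05 Simon test against 22.5% in MSS/pMMR patients: futility boundary 5 or fewer of the first 19, success at 18+ of 57. For a larger achieved N use 19+ (58-61) or 20+ (62-64), and note that power is slightly below 80% at 58, 59 and 62.
- Label the ordinary 95% CI descriptive and name its method.
- Exempt the primary test from the two-sided sentence in SAP section 6.
- Say whether the 64 are MSS/pMMR only.

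Only if no look was made, replace the Simon claim in Protocol 3.2 and SAP section 1 with the single-stage exact rule, 19+ of 57 (alpha 4.0%, power 87.8%), and restate alpha and power. This replaces the stated basis for N, so it is more than rewording. Because 18 of 57 passes the first rule and fails the second, fix and date the choice before response data are reviewed.

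**Cost.** No extra patients. The two-stage rule carries the early futility stop that the named design already implies: 75.8% at a true 22.5% and 16.3% at a true 40%. It also needs a statement on patients accrued while stage-1 pathology is pending. Five two-week cycles take 8 weeks to the start of the last cycle and 10 to its end, and "Surgery was scheduled within 4-6 weeks after the last cycle of therapy", so pathology comes about 12 to 16 weeks after treatment starts.

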10.2.4. Secondary Study Endpoint Analysis

For the temporal event data (DFS, OS) in the secondary endpoints, Kaplan-Meier was used to estimate the median value, estimate the 95%CI of the median DFS/OS, plot a survival curve, and estimate the 2-year disease-free survival and its 95%CI.

Statistical rates and 95%CI were pooled for binary data in secondary endpoints (tumor pathological downphase rate, pCR rate, and R0 removal rate).

10.2.5. Safety Analysis

10.2.5.1. Adverse event analysis

Adverse events will be coded using MedDRA (v23.0 or higher) as low-level terms, preferred terms, and major System organ Class (SOC).

An adverse event occurring during treatment (TEAE) is defined as any adverse event that occurs after initiation of the investigational drug. Data on AE, SAE, grade ≥ 3 AE, grade ≥ 3 SAE, drug-related AE, drug-related AE, incidence $\geq 5\%$, incidence $\geq 5\%$, AE leading to dose adjustment, AE leading to termination of treatment, and AE related to surgery were statistically summarized.

Statistic Analysis Plan

Title of study	Neoadjuvant chemotherapy combined with camrelizumab and apatinib in patients with locally advanced colon cancer: a single-arm, prospective study
NCT number	NCT04625803
Institution	The First Affiliated Hospital, Zhejiang University School of Medicine
major investigators	[name] [name]
Protocol No.	MA-CRC-II-004
Version	1.3
Version Date:	07 November 2021

1.sample size

This was a single-arm study, and no randomization was used. To determine the sample size, we used the Simon 2-stage optimum design with a unilateral alpha of 0.05 to achieve a power of 0.8, and the pathological response rate (TRG 2-4) was expected to increase from 22.5% to 40%. Considering a 10% shedding rate, it was estimated that 64 patients needed to be enrolled.

2. Subject Distribution

Descriptive analysis of subject distribution, including but not limited to enrollment, withdrawal, and major protocol violations. The reasons for screening failure and the reasons for quitting the test were summarized.

3. Demographic and Other Disease Characteristics

Descriptive statistics were performed on sociodemographic characteristics and other disease characteristics. Sociodemographic characteristics include age, sex, etc. Other characteristics include tumor history and past medical history.

4. Analysis of Primary Study Endpoint

The primary endpoint of this study is pathological response rate, which will be aggregated and its 95%CI.

5. Secondary Study Endpoint Analysis

For the temporal event data (DFS, OS) in the secondary endpoints, Kaplan-Meier was used to estimate the median value, estimate the 95%CI of the median DFS/OS, plot a survival curve, and estimate the 2-year disease-free survival and its 95%CI.

Statistical rates and 95%CI were pooled for binary data in secondary endpoints (tumor pathological downphase rate, pCR rate, and R0 removal rate).

6. Safety Analysis

All the statistical analyses were performed using SPSS Statistics 26 (IBM, Armonk, NY, USA). Continuous variables with parametric distributions were evaluated using t tests. Categorical variables were evaluated using the chi-square test (or Fisher's exact test where appropriate). All the statistical tests were two-sided, and the significance threshold for all the P values was 0.05. Graphs were generated using GraphPad Prism (version 10.1.1).
